#### 10. SAFETY ANALYSES

The Safety Analysis Set will be used for all safety analyses. All data will be summarized as observed and no data imputation will be performed. No statistical treatment group comparison will be performed, unless otherwise specified.

#### 10.1. Adverse Events

Adverse events will be coded using MedDRA version 19.0. If a subject experiences multiple events that map to a single preferred term, the greatest severity and strongest investigator assessment of relationship to study drug will be reported for the applicable summaries.

Treatment-emergent adverse events (TEAE) are defined as events for which the date/time of onset is on or after the date of first dose of study drug. Where an AE with a partially or fully missing start date or time, and it is unclear as to whether the AE is treatment emergent, it will assume treatment emergent unless the CRF question "Did AE onset occur before the first dose of study drug (Yes/No)?" indicates otherwise.

The number and percentage of subjects with adverse events will be summarized by treatment group. System organ class will be sorted alphabetically and preferred term within each SOC will be sorted by overall descending order of frequency. Subjects will be counted only once for each SOC and PT. The percentages will be calculated based on the number of subjects in each treatment group of the Safety analysis set.

Final 1.0 March 13, 2019 Ocular and non-ocular adverse events will also be summarized.

All adverse events (treatment-emergent and non-treatment-emergent) will be listed.

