9.2 Adverse Events and Serious Adverse Events

9.2.1 Adverse Events

Adverse Event

An AE is any untoward medical occurrence in a patient or clinical investigation patient administered a study drug, which does not necessarily have a causal relationship with this treatment. An AE can therefore be any unfavorable and unintended sign (including an abnormal laboratory finding), symptom, or disease temporally associated with the use of the study drug whether or not it is considered related to the study drug. AEs will be collected from the time the subject signs the informed consent form through 30 days after the last study drug administration.

Abnormal laboratory and other abnormal investigational findings (i.e., physical exam) should not be reported as AEs unless they are associated with clinical signs and symptoms, lead to treatment discontinuation or are otherwise considered clinically relevant by the investigator. In cases of surgical or diagnostic procedures, the condition/illness leading to such a procedure is considered as the AE rather than the procedure itself. In case of a fatality, the cause of death is considered as the AE, and the death is considered as its outcome.

Events Not to Be Considered as Adverse Events

Pre-existing medical conditions/signs/symptoms present before the screening period that do not worsen in severity or frequency during the study are defined as baseline medical conditions, and are not to be considered AEs.

All AEs must be recorded in the site's study records and the AE CRF with the following information:

1. Relationship to Study Drug: The Investigator must assess whether they consider an AE to be drug-related. In assessing this relationship, the Investigator must use information about the drug as outlined in the Investigator's Brochure (IB), the subject's pre-existent medical conditions/concurrent medication, and chronology of the event relative to drug administration.

The following definitions will be used:

- **Definitely or possibly related** applies to those AEs that, after careful medical consideration at the time they are evaluated, are considered by the Investigator (or other qualified physician) to have at least a possible relationship to study drug.

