9.2.2 Treatment Emergent Adverse Events (TEAE)

A TEAE will be an AE that occurred during the study after the first dose of study drug or that was present prior to dosing and exacerbates after the first dose of study drug.

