10.8.1 Adverse Events

AEs will be coded by the Medical Dictionary for Regulatory Activities (MedDRA) preferred terms, and all summary tables for AEs will be organized by these categories. Frequency counts and percentages will be presented for subjects with AEs within each system organ class and preferred term, separated by treatment arm. Both subjects ever experiencing an event as well as total events will be presented. Descriptive statistics will also be presented for AE relationship and AE severity. If multiple intensities are reported for a given AE for a subject, the most severe intensity will be counted.

SAEs and TEAEs that resulted in termination of the study drug and withdrawal from the study will be presented.

11 Direct Access to Source Data/Documents

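### The SAP flags treatment-emergent AEs by onset on or after the calendar date of first dose and drops the protocol's worsening clause, an undeclared change that can misclassify some events

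*SAP*

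**What the plan says.** Protocol 9.2.2 gives a two-part definition. A TEAE is "an AE that occurred during the study after the first dose of study drug", or one "that was present prior to dosing and exacerbates after the first dose of study drug".

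SAP 10.1 has one part only: "events for which the date/time of onset is on or after the date of first dose of study drug". Worsening is not mentioned. A fallback covers an AE with a "partially or fully missing start date or time, and it is unclear as to whether the AE is treatment emergent". Such an AE is assumed treatment-emergent unless a CRF item on whether onset preceded the first dose says otherwise.

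SAP Section 11 lists two changes from the protocol, to the ITT and PP definitions. The TEAE definition is not among them.

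On collection, Protocol 9.2.1 says "AEs will be collected from the time the subject signs the informed consent form through 30 days after the last study drug administration". It also asks for start and end dates and times, and for changes in severity to be assessed at each visit.

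**The concern.** There are two departures from the protocol.

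First, the SAP's reference point is a calendar date and not the dose. Consent, the screening examinations, randomization and dispensing all belong to Visit 1 on Day 1 (Protocol 5.4.1). The examinations include fluorescein at the slit lamp, pupil dilation and a blood draw. AEs are collected from consent, so an event can be recorded before any drug has been given and still carry the first-dose date.

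Second, the SAP has no route by which an AE that began before the first-dose date and worsened on drug becomes treatment-emergent.

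The flag feeds most of the AE reporting in SAP 10.1.1 to 10.1.6: incidence by system organ class and preferred term, relationship, severity, serious events and events leading to discontinuation. It also feeds the Fisher tests for preferred terms reaching 10% in either arm. An undeclared change of definition means that two analysts, one following the protocol and one the SAP, could produce different tables.

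**Working it through.** The plan has no figure to reproduce here, so the check applies both rules to the possible timings of an AE.

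Inputs:
- Protocol rule (9.2.2): TEAE if onset is after the first dose, or if the AE was present before dosing and worsened after it.
- SAP rule (10.1), read literally: TEAE if the onset date is on or after the first-dose date.
- SAP 3.2.8: the first-dose date is Day 1.
- Start dates and times are known in every pattern, so the missing-date fallback does not apply.

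| Pattern | Protocol | SAP | Result |
|---|---|---|---|
| A. Onset before the first-dose date, worsens after dosing, original onset date kept | TEAE | not TEAE | SAP misses it |
| B. As A, but the worsening is entered as a new AE with its own date | TEAE | TEAE | agree |
| C. Onset on Day 1 before the dose, no worsening | not TEAE | TEAE | SAP adds it |
| D. Onset on Day 1 before the dose, then worsens | TEAE | TEAE | agree |
| E. Onset on Day 1 after the dose | TEAE | TEAE | agree |

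The rules differ in 2 of 5 patterns, once in each direction. This is a count of patterns, not of events.

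**Pattern C** needs only a first dose on the day of Visit 1 and an AE between consent and that dose. The fallback can remove such an AE when its start time is missing and the CRF item places onset before the dose. The same AE with a complete time falls outside the fallback and is counted. The more fully recorded event is therefore the one misclassified.

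**Pattern A** needs two conditions. The AE must be dated before the first-dose date. That is possible because drug is taken at home (Protocol 7.5), one repeat of a test is allowed (6.2) and one rescreening is allowed (5.4.1). The worsening must also keep the original onset date. Neither document says how a worsening is dated. Protocol 10.8.1 says "If multiple intensities are reported for a given AE for a subject, the most severe intensity will be counted", which shows that one AE may carry several severities. It is a tabulation rule and does not settle the onset date.

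Scale, from 60 per arm (SAP 2.3.6):
- One reclassified subject: 1/60 = 1.7 percentage points.
- 10% trigger for a Fisher test (SAP 10.1.2): 0.10 × 60 = 6 subjects.

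For a preferred term near the trigger, a single subject can decide whether the test is run.

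**The case against.** The strongest reply is that little rests on the flag.

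- The primary safety endpoint is all AEs reported (SAP 2.2.2.1). SAP 10.1.1 counts subjects with any AE and total AEs, and all AEs are listed whether treatment-emergent or not. This stands. A reader might infer that the trial's main safety count is wrong in both directions. The documents do not support that: those outputs do not use the flag, and no miscount has been shown.
- For AEs arising on a Day 1 when dosing also starts, the two errors do not occur together. Every AE that day is counted, including one that later worsens, so the missing clause loses none of them. If dosing starts on a later date, the Day 1 AEs are not added. This stands and narrows the undercount.
- Conditions present before screening are AEs only if they worsen (Protocol 9.2.1). If the worsening is entered with its own date, the SAP counts it. A reader might infer that worsened pre-dose events are never captured. That follows only if the original date is kept, which the documents leave open.
- Worsening in the eye also appears in the by-visit summaries of slit-lamp findings, visual acuity, IOP and fundus (SAP 9.3.1, 9.3.3, 10.2.1, 10.2.2). This is true, but they do not replace AE reporting.
- Events before the first dose of masked drug cannot be caused by it, so pattern C adds noise and does not hide harm. The protocol synopsis treats safety tests as exploratory. Both points limit the consequence.

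None of this explains why the SAP differs from Protocol 9.2.2 or why Section 11 is silent.

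**Conclusion.** SAP 10.1 departs from Protocol 9.2.2 in its cut-off and in omitting worsening, and the change is not declared. The overcount follows from the wording for any subject first dosed on the day of Visit 1 who has a pre-dose AE that day with a complete date and time and no later worsening. The undercount is conditional on an onset before the first-dose date and on the worsening keeping that date.

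The outputs affected are the TEAE tables and the exploratory Fisher tests for terms at 10% or more. The all-AE counts and the listing are unaffected. The number of events cannot be estimated from the documents; the figure of 1.7 percentage points per subject is a scale only and assumes 60 per arm.

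It might also seem to follow that the CRF Yes/No answer should govern every AE. The protocol does not require that, and it would let a tick-box override complete recorded dates and times.

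**What to change.** In SAP 10.1:

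1. Restore the two-part definition of Protocol 9.2.2: onset after the first dose, or present before dosing and exacerbating after it.
2. Compare onset with the date and time of first dose. For an AE dated on the first-dose date whose order relative to the dose is not settled by recorded times, use the existing CRF question on pre-dose onset.
3. State that a post-dose worsening of a pre-dose AE is flagged as treatment-emergent whatever its original onset date.

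If the sponsor prefers the present rule, it should be listed and justified in Section 11.

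The cost is a few sentences and some programming of the flag. AE start times are required by Protocol 9.2.1, and the diary records the time of each dose (Protocol 7.5). SAP 6.2.1 describes the diary eCRF by date only, so it should be checked that first-dose time is in the database; step 2 covers the case where it is not. The small downside is that the worsening part needs the timing of severity changes from the AE records. The protocol requires those changes to be assessed at each visit, but the documents do not show how the AE form stores them.

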#### 10.1.1. Overall Adverse Events

The number and percentage of subjects with at least one adverse event will be summarized by treatment group for the following:

- Subjects with and without any adverse event
- Total number of adverse event
- Subjects with and without any treatment-emergent adverse event
- Total number of treatment-emergent adverse event
- Subjects with severe treatment-emergent adverse event
- Subjects with any study drug related treatment-emergent adverse event
- Any treatment-emergent adverse event leading to study drug discontinuation / study termination
- Subjects with any treatment-emergent serious adverse event (SAE)
- Subjects with any study drug related treatment-emergent serious adverse event
- Subjects with outcome of death

#### 10.1.2. Incidence of Adverse Events

Subjects with at least one treatment-emergent adverse event will be summarized by SOC, PT, and by treatment group. Treatment-emergent adverse event that treated by rescue medications will also be summarized by SOC, PT, and by treatment group.

Treatment-emergent adverse event summary by PT with descending order of frequency in the Total group will also be presented by treatment group. For PT with  $\geq 10\%$  occurrence in any treatment group, Fisher's exact test will be used for the treatment group comparison.

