# 2.3.4.3. Rescue Therapy

Rescue therapy will be administered after completion of the Week 1 or Week 2 assessments if any one of the below criteria are met:

- Worsening of visual acuity due, in the opinion of the Investigator, to non-infectious anterior uveitis by  $\geq 2$  lines or  $\geq 10$  letters using ETDRS testing from **Day 1** to **Week 1** or any time after **Week 1** (compared to Day 1)
- Subject demonstrates one unit or more increase in ACC grade from **Day 1** to **Week 1** or any time after **Week 1** (compared to Day 1)
- Subject fails to show improvement in ACC grade from Day 1 to Week 2

The protocol recommended rescue therapy is Durezol® (difluprednate ophthalmic emulsion 0.05%) four times a day (QID) plus Cyclogyl (cyclopentolate hydrochloride ophthalmic solution, 1%) up to QID, as needed (PRN). Durezol® tapered to three times a day (TID), twice a day (BID), once a day (QD) each subsequent week if ocular exam and symptoms improve. Alternative rescue therapy may be given at the discretion of the Investigator.

Once it is determined that rescue therapy is needed, the subject should be considered an Early Termination and the Week 4 (Visit 6) assessments should be completed.

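### Adverse events that begin after rescue are tabulated and tested under the study-drug arm, and no planned table separates them

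*SAP*

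**What the plan says.** SAP 10.1 defines treatment-emergent events as "events for which the date/time of onset is on or after the date of first dose of study drug". It sets no end at the last dose or at rescue. Protocol 9.2.2 likewise has no stop at rescue: "A TEAE will be an AE that occurred during the study after the first dose of study drug".

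Protocol 9.2.1 fixes the collection window: "AEs will be collected from the time the subject signs the informed consent form through 30 days after the last study drug administration".

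On rescue, SAP 2.3.4.3 says: "Rescue therapy will be administered after completion of the Week 1 or Week 2 assessments", if any one of its criteria is met. Those criteria are loss of visual acuity, a rise in anterior chamber cell grade, or no improvement in that grade by Week 2. The recommended rescue is a topical steroid ("difluprednate ophthalmic emulsion 0.05"%) stepped down weekly, plus a cycloplegic as needed; the investigator may choose an alternative. The rescued subject becomes an early termination. The per-protocol definition (SAP 3.1.2) confirms that rescue entails withdrawal of study medication.

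SAP 10.1.2 gives the main incidence table: "Subjects with at least one treatment-emergent adverse event will be summarized by SOC, PT, and by treatment group". Preferred terms at 10% or more in either group get a Fisher's exact test. The same section also tabulates events that were treated with rescue medication. SAP 10.1.3 splits events by the investigator's judgment of relatedness to study drug. The Safety set is analyzed by treatment received (SAP 3.1.3), and rescue does not move a subject out of the study-drug group.

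**The concern.** After rescue, a subject is off study drug and on other active eye drops. Any event that starts then still meets the treatment-emergent definition and enters the incidence, severity and relationship tables under ADX-102 or vehicle. Because SAP 10.1 reports the greatest severity and strongest relationship within a preferred term, a recurrence after rescue can also upgrade an event that began on study drug.

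The two tables that come closest do not isolate these events. One selects by how an event was treated, not by when it began. The other depends on masked judgment about study drug, and under SAP 10.1.3 a missing relationship counts as related.

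Safety is part of the secondary objective, and adverse events are the primary safety endpoint (SAP 2.2.2.1). If ADX-102 works as assumed, more vehicle subjects would be expected to meet the rescue criteria. Rescue-drug events would then accumulate in the comparator, and a real ADX-102 excess in a shared term could look smaller than it is.

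**Working it through.** **Figures in the plan.** The documents give no expected adverse-event or rescue rate, so there is no stated safety figure to reproduce. The relevant planning figure is the efficacy assumption in SAP 2.3.6: success hazards of 0.2672 and 0.1098, ratio 2.434, with 53% censored. With Schoenfeld's formula, power = Φ(√(d/4)·ln 2.434 − 1.96):
- N = 90: d = 0.47 × 90 = 42.3 events, power 82.4% (stated 82%).
- N = 120: d = 0.47 × 120 = 56.4 events, power 91.6% (stated 91%).

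The assumption is internally consistent and nothing here changes it. It suggests more rescue on vehicle but does not quantify it.

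**Share of the collection window after the last dose**, assuming the last dose falls on the rescue day:

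| Subject | Calculation | Share |
|---|---|---|
| Rescued Day 8 | 30/(8+30) | 79% |
| Rescued Day 15 | 30/(15+30) | 67% |
| Completer, last dose Day 29 | 30/(29+30) | 51% |

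Every subject has the 30-day tail. What sets a rescued subject apart is that the tail is spent largely on rescue therapy. Counted only to the Day 36 telephone call, the post-rescue shares are (36−8)/36 = 78% and (36−15)/36 = 58%.

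**Effect on one preferred term, no study-drug effect.** Let b be the background rate, r the rescue rate in an arm, and q the chance that rescue therapy causes the term in a rescued subject. Reported rate = 1 − (1−b)(1−rq). All three inputs are assumptions: b = 5%, with r and q varied. The arm difference reduces to 0.95 × q × (r on vehicle − r on ADX-102).

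| q | Rescue 20% vs 20% | 20% vs 40% | 20% vs 60% |
|---|---|---|---|
| 5% | 0 | 1.0 points | 1.9 |
| 10% | 0 | 1.9 | 3.8 |
| 20% | 0 | 3.8 | 7.6 |
| 30% | 0 | 5.7 | 11.4 |

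Vehicle looks worse in every non-zero cell. With 60 per arm, the 20% vs 40% column is about 0.6 to 3.4 subjects (60 × 0.0095 to 60 × 0.057).

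**Masking a true excess.** Suppose ADX-102 truly adds 8 points (13% vs 5%). The reported excess is [1 − 0.87(1 − rq)] on ADX-102 minus [1 − 0.95(1 − rq)] on vehicle, each with its own r:
- 20% vs 40%, q = 10%: 14.7% − 8.8% = 5.9 points.
- 20% vs 40%, q = 20%: 16.5% − 12.6% = 3.9 points.
- 20% vs 60%, q = 20%: 16.5% − 16.4% = 0.1 points.
- 20% vs 20%, q = 20%: 0.08 × (1 − 0.04) = 7.7 points, so equal rescue dilutes only slightly.

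**Would a crude pre-rescue table be better as the lead?** Assume the same 10% risk over 59 days in both arms at a constant hazard, with rescue at Day 8. The 8-day risk is 1 − 0.9^(8/59) = 1.42%. With rescue of 20% vs 40%, ADX-102 shows 0.8 × 10% + 0.2 × 1.42% = 8.3% and vehicle 0.6 × 10% + 0.4 × 1.42% = 6.6%. With 45% on vehicle, that arm shows 6.1%. Cutting at rescue without adjusting for follow-up thus creates a false ADX-102 excess.

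**The case against.** The strongest reply is that all-event incidence is a defensible lead presentation and that the plan already offers help. Protocol 9.2.1 tells investigators to weigh concurrent medication and timing when judging relatedness, and SAP 10.1.3 tabulates the result. All events are listed (SAP 10.1), rescued subjects are listed (Protocol 10.6.1), and rescue therapies are summarized (SAP 8.2). The Synopsis calls the safety tests exploratory. After the early-termination visit the only scheduled contact is one telephone call, so fewer events may be captured than the calendar window implies. The model above also gives a rescued subject the same background risk as a completer, and effective rescue could prevent disease-related events on vehicle.

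Most of this stands. It supports keeping the all-event tables as the lead and reading the sizes as illustrations. It does not supply a table split at rescue.

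Three stronger readings are tempting and not supported:
- That rescue therapy does differ by arm, so the bias is a fact. No rescue rate by arm is given; Time to Rescue is only listed as an endpoint to be compared.
- That the whole safety comparison is affected. Eye pressure, fundus, laboratory and vital-sign assessments are done at the early-termination visit (Protocol 5.4.4), and none is scheduled later.
- That pre-rescue events should replace all events as the basis of the Fisher tests. The last calculation shows that this exchanges one bias for another.

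**Conclusion.** The gap is real and limited: post-rescue events are counted under the study-drug arm, and nothing planned isolates them by onset. The possible consequence is dilution or masking of an ADX-102 excess in terms that rescue therapy also causes. This depends on rescue being more frequent on vehicle, which is plausible from the efficacy assumption but unquantified. At a 5% background rate and 20% versus 40% rescue, the shift is about 1 to 6 points for a rescue-caused chance of 5% to 30% per term. It is zero if rescue is equal and there is no study-drug effect. No power or sample-size figure is affected. This is an inexpensive improvement to interpretation; it does not make the planned tables invalid.

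**What to change.** Amend SAP 10.1 before unmasking:
1. Keep the all-event tables and Fisher tests as the lead presentation.
2. Flag each treatment-emergent event as starting before, or on or after, the first rescue dose. Where there is no rescue dose, use the date of discontinuation due to the need for rescue, as in SAP Table 8. Order same-day events by recorded time.
3. Add supportive tables by arm for each period, with exposure time and exposure-adjusted incidence rates as well as counts and percentages. The post-rescue table compares subjects selected by outcome, so keep it descriptive.
4. Mark post-rescue onset in the adverse-event listing.

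Event start dates and times are already collected (Protocol 9.2.1), and the rescue date is already needed for Time to Rescue. The cost is SAP wording, one derived flag and one extra set of tables. Rescued subjects have shorter pre-rescue follow-up. The exposure-adjusted rates address this, provided the event rate is roughly constant over time, and the SAP should state that assumption.
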